4.2 Obtaining Identifiable Information About Non-Subjects

N/A

4.3 Number of Subjects

A. Total Number of Subjects

We expected to screen 100 individuals. Seventy will be eligible and consent for participation. We need 60 individuals to complete the study.

B. Total Number of Subjects If Multicenter Study

N/A

C. Feasibility

[name] has a long history of working with local community partners to recruit study participants.

4.4 Consent Procedures

A. Consent Process

▪ **Location of Consent Process**

Written consent at the recruitment sites.

▪ **Ongoing Consent**

N/A

▪ **Individual Roles for Researchers Involved in Consent**

All participants will have a copy of the consent form to keep for their records. Research staff will be available to answer questions about the consent form when the participants are reading it, and they will also answer any questions that are raised later in the process (e.g., during the assessment, experimental session, or follow up).

▪ **Consent Discussion Duration**

Research staff will be available to answer questions about the consent form when the participants are reading it, and they will also answer any questions that are raised later in the process (e.g., during the assessment, experimental session, or follow up).

▪ **Coercion or Undue Influence**

In the consent form, we explain the voluntary nature of participation, any alternatives to participating, the ability to withdraw at any time

▪ **Subject Understanding**

Staff will ask participants to describe briefly the study procedure.

▪ **Protecting Privacy**

Individuals will have their own privacy while reading the consent. Research staff will be available if they have any questions.

B. Waiver or Alteration of Consent Process

N/A

UPLOAD to e-IRB Section 13.17 Consent Form - The consent form(s) and consent script(s) you plan to use to inform and consent individuals to take part in the research.

C. Documentation of Consent

▪ **Documenting Consent**

We will ask participants to sing the consent document. All participants will have a copy of the consent form to keep for their records.

• **Waiver of Documentation of Consent (i.e., will not obtain subject's signature)**

N/A

4.5 Special Consent Populations

N/A

4.6 Economic Burden and/or Compensation for Subjects

A. Expenses

Costs to participants may include transportation to the study site to complete consent, the baseline survey and neuroimaging experiment. In return for participants' time and effort, they will be paid compensations for completion of the baseline survey and neuroimaging experiment.

B. Compensation/Incentives

Participants will receive \$ 85.00 in the form of visa gift cards for taking part in this study according to the following schedule:

- \$ 15.00 to complete the first survey
- \$ 60.00 at your study visit
- \$ 10.00 to complete the follow-up survey.

C Compensation Documentation

We will document study ID with payment amount, date and signature of the research staff who issued the payment.

4.7 Risks of Harm/Potential for Benefits to Subjects

A. Description of Risks of Harm to Subjects

▪ Reasonably Foreseeable Risks of Harm

There is a risk of discomfort associated with answering sensitive survey questions about their behaviors as part of the behavioral surveys. We will explain the nature of the questions to be asked during the consent process and all participants will be able to refuse to answer any questions or terminate the survey at any time. There is also a small potential risk of loss of confidentiality in all research, but risk to participants will be minimized by training all staff in the ethical conduct of research and the strict protection of the data through using password protected databases and double-locked cabinets to written consent forms, which will have participants' signature. Data will only be shared following secure transfer.

There are no known risks associated with the use of fNIRS, which employs harmless light sources, fNIRS is safe for studies with infants and adults as well. However, participants may feel uncomfortable wearing the headband connected to fNIRS. They may also experience fatigue from looking at a computer screen while wearing the headband.

▪ Risk of Harm from an Intervention on a Subject with an Existing Condition

None

▪ Other Foreseeable Risks of Harm

None

▪ Observation and Sensitive Information

N/A

B. Procedures which Risk Harm to Embryo, Fetus, and/or Pregnant Subjects

N/A

C. Risks of Harm to Non-Subjects

N/A

D. Assessment of Social Behavior Considerations

All study staff undergo a training facilitated by an expert in Crisis Response to recognize signs of suicidal behavior or ideation and other psychological disturbances and appropriate procedures to follow in these cases.

E. Minimizing Risks of Harm

Research participants will be protected against discomfort and loss of confidentiality as much as possible by conducting all study procedure in private and comfortable locations. Risk to subjects will be minimized by: 1) training all staff in the ethical conduct of research; 2) strict protection of confidentiality through detailed standard operating procedures and on-site monitoring; 3) careful handling of sensitive data, procedures and processes in place to ensure data are securely stored and transferred; and 4) referral of participants to professionals or community agencies with medical health training or other appropriate services when necessary. While the potential risks to subjects are low, any social harm will be reported to the PI and a serious event will be reported to the Rutgers IRBs within 24 hours.

Should any participant experience discomfort or distress from participation in the study, we will provide the participant with the appropriate referral needed for follow-up and care.

All research staff will undergo extensive training prior to beginning the study, including training on issues of confidentiality. In addition, all study staff members will be trained in ethical conduct of research. Data containing identifiers will be stored on Rutgers' secure servers.

Furthermore, privacy and confidentiality will be protected in several ways: 1) survey responses will be captured on the highly secure server, only with participants' study ID; 2) no subject will be identified in any report or publication; 3) all study materials and data collection forms will be kept in locked and password protected files; 4) data will be analyzed collectively and individual participant data will remain anonymous.

- **Certificate of Confidentiality**

This study is NIH-funded for which a Certificate of Confidentiality is automatically issued to protect the data obtained.

- **Provisions to Protect the Privacy Interests of Subjects**

F. Potential Direct Benefits to Subjects

The most important direct benefit of participating in this study is that participants may initiate PrEP after being exposed to the PrEP promotion messages. Potential indirect benefits include psychological and social support, where staff will make appropriate referrals for psychological and social support services in their area. Another potential benefit is that participants may experience the altruistic benefit of participating in a study that contributes to health of MSM, ultimately strengthening the MSM community in the US.

5.0 Special Considerations

5.1 Health Insurance Portability and Accountability Act (HIPAA)

N/A.

5.2 Family Educational Rights and Privacy Act (FERPA)
N/A.

5.3 Code of Federal Regulations Title 45 Part 46 (Vulnerable Populations)
N/A.

A. Special Populations

N/A.

5.4 General Data Protection Regulation (GDPR)
N/A.

5.5 NJ Access to Medical Research Act (Surrogate Consent)
N/A.

6.0 Data Management Plan

6.1 Data Analysis

Our primary aim in this study is to assess the effectiveness of PrEP promotion messages developed via open contest by assessing brain activation in the regions associated with persuasion (i.e., Medial Prefrontal Cortex (MPFC)), and any changes in participants' PrEP willingness, behavioral intention, initiation, and action in 30-day follow up. We will first assess whether the randomization has worked by comparing baseline demographic and confounding variables of participants in each arm using Fisher's exact test for dichotomous variables, analysis of variance (ANOVA) tests for nominal variables and normally distributed continuous variables, and Wilcoxon signed-rank tests for non-normally distributed continuous variables, with statistical significance determined at alpha=0.05. Any variable for which randomization did not result in equal proportions in each arm will be incorporated into the multivariate models as a potential confounding variable.

Next, we will conduct primary inferential analyses to compare a) the level of neural activity in MPFC, b) increase in willingness and behavioral intention to take PrEP between baseline and 30-day follow up (yes/no), and c) PrEP action and initiation at 30-day follow up (yes/no) among participants in the three conditions. fNIRS detects the ratio of oxygenated (O₂HB) to deoxygenated (HHB) hemoglobin based on their optical properties, with higher ratios indicating greater neural activity. By modulating light at different wavelengths, emitting the light on the skin-exposed areas of the cranium, and detecting that light, fNIRS measures the blood oxygenation level dependent signal (BOLD) similar to fMRI. Because the photons reflected from neural tissue follow a reliable 'banana-shaped' path, photodetectors can be used to measure this on the scalp. By measuring the amount of absorbed light directed at the neural tissue, we can measure the amount of O₂HB and HHB present in a region of the brain at a given time and draw inferences about the level of neural activity. The level of brain activation for the top message condition compared to references will be evaluated using pairwise comparison. For the binary outcome measures, increase in willingness and behavioral intention to take PrEP and PrEP action and initiation, we will first compare proportions by conditions separately for each measurement period using standard bivariate analytic techniques such as Spearman rank-order correlations, odds ratios, and Fisher's exact test. Then we will employ generalized linear mixed

models (GLMM) to evaluate the effectiveness of top messages developed via open contest. GLMM permits us to measure the fixed effect of the top messages developed via open contest on neural activity, willingness and behavioral intention to take PrEP, and PrEP action and initiation, while allowing a random effect that accounts for within-person correlation. Given the binary nature of two primary outcomes, we will specify a logit link function for our GLMM models. Comparisons of characteristics of participants who are lost to follow-up to those who are evaluated will be conducted to assess for systematic patterns that could influence results.

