1.3 Research Design and Methods

This study is a randomized control trial (RCT). A total of 60 participants will be recruited and enrolled into this RCT where half of them will view PrEP promotion messages developed via a crowdsourcing open contact¹ and half of them will view PrEP promotion messages developed via social marketing.

A. Research Procedures

This study will be conducted as follows:

- Screening will be conducted in person after an oral consent. Once an individual is screened eligible, he will provide an informed consent and complete a baseline survey. A 2nd in-person visit will be scheduled, roughly a week after completing the baseline survey.
- During the in-person visit, participants will be randomized to one of two conditions: a) viewing top three messages developed by an open contest implemented in Baltimore, or b) viewing PrEP campaign messages that were developed with a traditional social marketing approach.
- After the randomization, a research assistant will take the participant to a private interview room. The research assistant will measure and fit the participant's head for the fNIRS headband, which is connected to a NIRSport. NIRSport is a portable fNIRS device to measure the neural response as participants view various messages on a computer screen with audio computer assistance. Similar to functional magnetic resonance imaging (fMRI), fNIRS is a non-invasive neuroimaging technique to measure key brain regions associated with influence and persuasion. Unlike fMRI, fNIRS only collects data ~3 cm into the cortex, yet the advantages of fNIRS are that it is small, portable, quiet, and does not require being still in a narrow tube. Employing harmless light sources, fNIRS is safe for studies with infants and adults as well. fNIRS involves wearing a lightweight cap from which LED lights are directed into the brain. The LED light emerges from the brain in predictable patterns and the way in which active brain tissue absorbs light allows us to reconstruct fMRI type images of the activity in the cortical surface. fNIRS have been widely used in social neuroscience research.
- Participants in each group will view multiple messages on a computer screen while brain activity is recorded.
- After completing all messages, participants will answer questions on perceived effectiveness of the messages, self-efficacy, and willingness and behavioral intention to use PrEP. Semi-structured questions on the acceptability of fNIRS will also be asked.

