1.5 Sample Size Justification

We aim to recruit 60 participants. In a recent systematic review of 20 studies that examined persuasive processing and outcomes of the health messages using neurocognitive measures,⁹ the sample size ranged from 14 to 91.⁵ Our primary goal for conducting this experimental study is to examine any preliminary evidence for the efficacy of an open contest approach to develop effective PrEP promotion messages. Effect-size estimates determined through this study will be essential in the design of a larger and fully powered efficacy study that tests intervention effects on PrEP uptake.

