1.6 Study Variables

A. Independent Variables, Interventions, or Predictor Variables

Intervention: top three messages developed by an open contest implemented in Baltimore¹.

B. Dependent Variables or Outcome Measures

Brain activity: fNIRS detects the ratio of oxygenated (O₂HB) to deoxygenated (HHB) hemoglobin based on their optical properties, with higher ratios indicating greater neural activity. Neural tissues are relatively transparent to light in the near infrared range between 700-1000 nm, and O₂HB and HHB reflect distinct wavelengths in this range. By modulating light at different wavelengths, emitting the light on the skin-exposed areas of the cranium, and detecting that light, fNIRS measures the blood oxygenation level dependent signal (BOLD) like fMRI. Because the photons reflected from neural tissue follow a reliable 'banana-shaped' path, photodetectors can be used to measure this on the scalp. By measuring the amount of absorbed light directed at the neural tissue, we can measure the amount of O₂HB and HHB present in a region of the brain at a given time and draw inferences about the level of neural activity.

PrEP-related beliefs, willingness, behavioral intention, and behavior:

All questions will be asked to participants at baseline (only to individuals aware of PrEP), at the in-person visit after reviewing all messages, and at the 30-day follow up, except questions on PrEP action and initiation, which will only be asked at the 30-day follow up.

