Behavioral Intention: We will assess behavioral intentions to actually begin PrEP based on a real-world situation. To do this, participants will be asked, “PrEP is currently available with a prescription from your doctor and research has shown that a majority of insurance companies cover most or all of the costs of PrEP. Do you plan to begin PrEP?” Response options range from “Yes, I will definitely begin taking PrEP” to “No, I definitely will not begin taking PrEP.”

PrEP action and initiation: Items include “Have you spoken with a provider about PrEP during the past 30 days?” and “Have you started taking PrEP during the past 30 days?”

Message-related measures:

All questions will be asked after participants finish reviewing all messages during the in-person visit.

Perceived effectiveness: Participants will be asked, on a 4-point Likert scale ranging from strongly disagree to strongly agree, to rate their agreement that the message is believable, new, unconvincing, important to them, helps them feel confident about using PrEP, would help their friends use PrEP, put thoughts in their mind about using PrEP.

Baseline survey

Socioeconomic status: We will collect data on age, highest level of education attained, housing, employment history, health insurance status, access to health care, sources and amount of personal and household income,

Sexual identity: We will use a question from our previous study which asks participants to choose from heterosexual/straight, bisexual, homosexual/gay/same-gender loving, or not sure/questioning.

Sexual history: number of sex partners, sex of the partners, condom use in the past 90 days

Social media use: Types of social media sites used for socializing, seeking sex partners, and seeking health-related information.

HIV testing history

- **Ethnographic Studies, Interviews, Or Observation:**

N/A

- **Subject Identifiers:**

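### Section 6.1 names a paired test for independent arms and ANOVA for nominal variables, and chooses adjustment covariates by chance imbalance under a loosely worded rule

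*Combined protocol and SAP*

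**What the plan says.** Section 1.3 describes a parallel design in which "participants will be randomized to one of two conditions". There are 60 people, half in each arm, with no matching.

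Section 6.1 opens by checking whether randomisation worked. Dichotomous variables get Fisher's exact test. Unordered categories share a method with well-behaved measurements: "analysis of variance (ANOVA) tests for nominal variables and normally distributed continuous variables". Skewed measurements are assigned a different procedure, namely "Wilcoxon signed-rank tests for non-normally distributed continuous variables". The threshold for every one of these checks is the same: "with statistical significance determined at alpha=0.05". The covariate rule comes next, in a sentence of its own: "Any variable for which randomization did not result in equal proportions in each arm will be incorporated into the multivariate models". It states no threshold, and no fixed covariate list appears anywhere in the documents.

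The selected variables go into the generalised linear mixed models for neural activity (H1), increase in willingness and intention (H2), and PrEP action and initiation (H3). The binary outcomes use a logit link. Simple unadjusted comparisons come before the models.

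Section 1.5 gives the purpose of the estimates: "Effect-size estimates determined through this study will be essential in the design of a larger and fully powered efficacy study".

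**The concern.** There are three faults in two adjoining sentences.

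- **Paired test, unpaired arms.** The signed-rank test needs pairs. With independent arms the pairing is whatever row order the file has, and with unequal arms the test cannot be computed. It may be a slip for rank-sum.
- **ANOVA for nominal variables.** Unordered categories have no numeric values, so the p-value depends on the codes assigned. Sexual identity (section 1.9), with four unordered options, is one such variable.
- **Selection by imbalance.** The rule can mean significant at 0.05 or numerically unequal, and proportions do not apply to continuous variables such as age. On the first reading a prognostic variable enters no more often than an irrelevant one. On the second nearly everything enters. Neither reading selects on prognosis, and two analysts following the text could fit very different models.

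The first two faults affect the baseline table and covariate selection, not the outcome tests. The third decides what is in the adjusted models, whose effect sizes are meant to inform a larger trial.

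**Working it through.** The plan gives no figure to reproduce here beyond the alpha of 0.05. Taken from the documents: 60 participants, half per arm. Assumed: no missing data, and 8 or 15 independent binary candidates at 50% prevalence unless stated. Section 1.9 lists about 15 baseline items if income is counted once and social media use as three; section 6.1 does not say which are tested.

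**1. Signed-rank test.** In one simulated data set of 30 v 30, 2,000 arbitrary re-pairings gave p from 0.0016 to 0.38; rank-sum gave the single value 0.059. Over 4,000 null data sets signed-rank rejected 4.7%, so the fault is an arbitrary answer, not inflated error. With 29 v 30 the test returns an error.

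**2. ANOVA on categories.** Constructed counts are 5/15/5/5 against 5/5/5/15. Over all 24 codings, p ran from 0.0017 to 0.233. Chi-square: expected counts are 5, 10, 5, 10 in each arm, so the statistic is 4 × 5²/10 = 10 on 3 df, p = 0.019, whatever the coding.

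**3. How often one binary variable enters (30 v 30).**
- p<0.05 reading: the actual size of Fisher's exact test is 0.0094, 0.0222, 0.0261 and 0.0274 at prevalence 10%, 20%, 30% and 50%.
- Literal reading: P(exactly equal) = Σ[Bin(30, p)]² = 0.174, 0.129, 0.112 and 0.103, so the variable enters with probability 0.826 to 0.897.

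**4. Expected number entering at 50% prevalence.**
- p<0.05 reading: 8 × 0.0274 = 0.22; 15 × 0.0274 = 0.41.
- Literal reading: 8 × 0.897 = 7.2; 15 × 0.897 = 13.5 (simulated 13.4).

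**5. Consequence of the p<0.05 reading.**
- H1, 0.5 SD effect: power 0.456 to 0.471, against 0.472 to 0.480 unadjusted. Type I error 0.045 to 0.048.
- H2/H3, a 50% binary covariate, 4,000 runs, rule v prespecified. Odds ratio 2: 0.517 v 0.517 (10% v 30% with the outcome) and 0.710 v 0.712 (20% v 50%). Odds ratio 4: 0.517 v 0.542 and 0.709 v 0.750. The gain from prespecifying is 0 to 4 points; a repeat simulation gave about −1 to 4.
- Type I error of the binary models: 0.046 to 0.072, the same range as unadjusted.

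**6. Consequence of the literal reading for the 30-day outcome.** If 10% to 40% of 60 report it (assumed), there are 6 to 24 events. Events per parameter, counting arm plus covariates, run from 6/(13.4 + 1) = 0.4 to 24/(7.2 + 1) = 2.9. With irrelevant covariates only, the model was not estimable in 35% to 63% of runs at 10%, 2% to 11% at 20%, and under 1% at 40%. In estimable runs with a true effect, the median log-odds ratio rose from 1.33–1.46 unadjusted to 1.62–2.01.

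**The case against.** The strongest defence is that the literal reading is not the natural one. The alpha of 0.05 stands in the sentence before the rule, and the tests would serve no purpose if any numerical difference triggered entry. On the significance reading few variables enter, error rates hold, and the unadjusted comparisons planned in section 6.1 are untouched. Section 1.5 seeks only preliminary evidence, and signed-rank is probably a slip. All of this stands, and it limits the weight of the point. It does not rescue a rule that selects covariates without regard to prognosis, nor wording that needs a guess about its threshold.

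Three stronger readings are tempting and not supported.

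- **That the trial's false-positive rate is inflated.** It is not under the p<0.05 reading, nor for H1 under either reading. Excess rejection in the sparse logistic models appeared only under the literal reading, with a likelihood-ratio test that the plan does not name.
- **That prespecification would rescue H1.** Simulated power reaches 0.59 with a covariate correlated 0.5 with the MPFC signal, but the documents identify no such covariate.
- **That up to 11 points of power are lost for H2 and H3.** That needs a continuous covariate with an odds ratio of 4 per SD. A 50% binary variable has an SD of 0.5, so this equals about 4² = 16 between groups, far from what a yes/no item could be expected to deliver.

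**Conclusion.** The point holds at moderate weight. The two test names are wrong as written, with no assumption needed. The covariate rule is ambiguous and, on its likelier reading, picks covariates by chance. The cost there is precision forgone, and only if a prognostic covariate exists, which the documents do not show: about 0 to 4 points of power for H2 and H3 under the assumed binary covariate. These figures take the full 30 v 30. For H2 fewer people are likely, because section 1.6 restricts the baseline items: "All questions will be asked to participants at baseline (only to individuals aware of PrEP").

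The serious consequences, overloaded 30-day models and exaggerated odds ratios, follow only if the words are taken literally. They matter because the estimates are meant to size a later trial, but the documents do not show that this reading is intended. The number of candidates, their prevalence and independence, and the event rates are all assumptions.

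**What to change.** Delete the imbalance-based selection rule and report baseline characteristics descriptively by arm. Name in advance a very short covariate set for each outcome, collected from all participants and expected to be prognostic for it:

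- **H1:** none, unless one can be justified.
- **H2:** for example access to health care, already among the baseline items in section 1.9 ("highest level of education attained, housing, employment history, health insurance status, access to health care"). PrEP awareness will not serve: the outcome is an increase from baseline, and only aware participants have a baseline measure, so awareness is constant in that model.
- **H3:** at most one, for example access to health care or PrEP awareness (which must be known to route the baseline items).

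Include these whatever their balance, report the unadjusted result alongside, and label the adjusted odds ratio as conditional, since it differs from the unadjusted one even without confounding. If between-arm baseline tests are kept, use Wilcoxon rank-sum for non-normal continuous variables and chi-square or Fisher-Freeman-Halton for nominal ones.

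The cost is SAP wording. A prespecified covariate that proves non-prognostic spends one degree of freedom (under 0.02 of H1 power in simulation: 0.466 v 0.472). For H3, arm plus one covariate leaves 6/2 = 3 to 24/2 = 12 events per parameter if 10% to 40% of 60 report the outcome (assumed), so even one covariate is close to the limit at the low end.
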